Urogenital symptoms may include vaginal itching, burning, dryness, dyspareunia (difficult or painful sexual intercourse), dysuria (painful or difficult urination), nocturia (waking at night to urinate), incontinence (the involuntary loss of urine), urine frequency, urine urgency, and UTI.

Primary Objective	Evaluation of the subjective effects of fCO ₂ laser therapy on overall urogenital symptoms.
Secondary Objective	Assess vaginal pH and bacteria, overall vaginal health, urinary symptoms, sexual function, UTI frequency, and mental health status.
Primary Outcome	The mean and median response to treatment as measured by the Patient Global Impression of Improvement (PGI-I) questionnaire
Secondary Outcomes	Change in vaginal pH and overall vaginal health on physical examination as measured by the Vaginal Health Inventory Score (VHIS) Change in urinary symptoms as measured by the Questionnaire for Urinary Incontinence Diagnosis (QUID), OAB symptoms as measured by the Overactive Bladder Questionnaire-Short Form (OAB-q SF), cough stress test and voiding diaries Change in sexual function, including dyspareunia symptoms, as measured by the Female Sexual Function Inventory (FSFI) Change in the frequency of UTI occurrences Change in mental health status as measured by the Generalized Anxiety Disorder Questionnaire (GAD-7) and Patient Health Questionnaire (PHQ-8) Change in life and sexual impact of vulvovaginal skin symptoms as measured by the Incontinence Quality of Life Questionnaire (I-QOL) Change in the presence of lactobacillus, assessed by vaginal swab
Primary Endpoint	Week 16 (4 weeks post-treatment).
Secondary Endpoints	Primary and secondary outcomes will be evaluated again at Visit 4 (6-month follow-up) Primary and secondary outcomes will be evaluated again at Visit 10 (36-month follow-up)

SECTION II: METHODOLOGY

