This is a prospective observational study of patients undergoing vaginal treatment with the fCO₂ laser for various urogenital symptoms. We anticipate enrolling approximately 100 women in this study. The majority of patients are expected to be recruited from the WUC and private Urology offices. Informed consent will be obtained before any study activities are conducted. Women who meet all of the eligibility criteria will be enrolled in the study. Three treatments with the fCO₂ laser to the vagina will be performed, approximately six weeks apart. The patient will follow up every three months for the first year, then every six months for the following two years, for a total of three years of follow-up.

At each follow-up visit, the patients will complete specified questionnaires. The patient will be offered a repeat treatment at 1, 2 and 3 years if initial treatment efficacy has decreased. A pelvic examination will be performed at Visits 4 (6-month follow up), 6 (12-month follow up), 8 (24-month follow up), and 10 (36-month follow up) and the clinician will complete a cough stress test and the VHIS, including vaginal pH.

Patients will be advised to refrain from:

- vaginal intercourse for 24 hours prior to all visits.
- starting vaginal or systemic hormone therapy or use of new vaginal lubricants during the first six months of the study.
- starting any other preventative therapies for UTIs including antibiotic suppression, cranberry supplements, or d-mannose during the first six months of the study.
- starting any new treatments (i.e. pharmacologic, physical therapy) for overactive bladder (OAB) or stress urinary incontinence (SUI) during the first six months of the study.

Study patients will not be compensated for their participation in the trial. However, all research related activities, specified on the table of events, will be provided at no cost to the study patient.

Inclusion/Exclusion Criteria

Inclusion criteria:

- Female
- ≥18 years and ≤90 years of age
- One or more of the following indications for fCO₂ laser treatment:
 - Genitourinary symptoms of menopause, including after natural, medically-induced, or surgical menopause
 - Vaginal dryness, burning, itching, or dyspareunia not related to menopause
 - Recurrent UTIs, defined as 4 or more in a year
 - Overactive bladder
- Must sign the informed consent form
- Must be willing to comply with the study protocol

Exclusion criteria:

- Contraindications to fCO₂ laser treatment, such as:

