Current medications and AEs will be assessed. Urine dipstick, and urine culture will be performed, if indicated. UTI symptoms will be assessed. The patient will complete a PGI-I for symptom improvement, VSQ, I-QOL, QUID, OAB-q SF, FSFI, GAD-7 and PHQ-8. A vaginal exam, including a cough stress test and VHIS, will be performed. A vaginal swab will be collected for wet mount and examined microscopically for presence of lactobacillus.

Visit 5 – 9 Month Follow up (3 months +/- 2 weeks after Visit 4)

Current medications and AEs will be assessed. Urine dipstick, and urine culture will be performed, if indicated. UTI symptoms will be assessed. The patient will complete a PGI-I for symptom improvement, VSQ, I-QOL, QUID, OAB-q SF, FSFI, GAD-7 and PHQ-8. The patient will complete a three-day voiding diary within 1 week prior to Visit 6, which will be collected at Visit 6.

Visit 6 – 1 Year Follow up (3 months +/- 2 weeks after Visit 5)

Current medications and AEs will be assessed. Urine dipstick, and urine culture will be performed, if indicated. UTI symptoms will be assessed. Urine pregnancy test will be done in women of childbearing capability. The patient will complete a PGI-I for symptom improvement, VSQ, I-QOL, QUID, OAB-q SF, FSFI, GAD-7, PHQ-8, and Perception of Monetary Value. A vaginal exam, including a cough stress test and VHIS, will be performed. A vaginal swab will be collected for wet mount and examined microscopically for presence of lactobacillus. If the patient feels her symptoms have returned and she requests a repeat treatment this will be discussed with the investigator. If the investigator determines, in his/her clinical judgment, a treatment is appropriate the fCO₂ laser treatment will be performed. The patient will score discomfort using the VAS. The provider will score the difficulty of administering the treatment using the VAS.

Visit 7 – 18 Month Follow up(6 months +/- 2 weeks after Visit 6)

Current medications and AEs will be assessed. Urine dipstick, and urine culture will be performed, if indicated. UTI symptoms will be assessed. The patient will complete a PGI-I for symptom improvement, VSQ, I-QOL, QUID, OAB-q SF, FSFI, GAD-7 and PHQ-8. The patient will complete a three-day voiding diary within 1 week prior to Visit 8, which will be collected at Visit 8.

Visit 8 – 2 Year Follow up (6 months +/- 2 weeks after Visit 7)

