Current medications and AEs will be assessed. Urine dipstick, and urine culture will be performed, if indicated. UTI symptoms will be assessed. Urine pregnancy test will be done in women of childbearing capability. The patient will complete a PGI-I for symptom improvement, VSQ, I-QOL, QUID, OAB-q SF, FSFI, GAD-7 and PHQ-8. A vaginal exam, including a cough stress test and VHIS, will be performed. A vaginal swab will be collected for wet mount and examined microscopically for presence of lactobacillus. If the patient feels her symptoms have returned and she requests a repeat treatment this will be discussed with the investigator. If the investigator determines, in his/her clinical judgment, a treatment is appropriate the fCO₂ laser treatment will be performed. The patient will score discomfort using the VAS. The provider will score the difficulty of administering the treatment using the VAS.

Visit 9 – 30 Month Follow up (6 months +/- 2 weeks after Visit 8)

Current medications and AEs will be assessed. Urine dipstick, and urine culture will be performed, if indicated. UTI symptoms will be assessed. The patient will complete a PGI-I for symptom improvement, VSQ, I-QOL, QUID, OAB-q SF, FSFI, GAD-7 and PHQ-8. The patient will complete a three-day voiding diary within 1 week prior to Visit 10, which will be collected at Visit 10.

Visit 10 – 3 Year Follow up (6 months +/- 2 weeks after Visit 9)

Current medications and AEs will be assessed. Urine dipstick, and urine culture will be performed, if indicated. UTI symptoms will be assessed. Urine pregnancy test will be done in women of childbearing capability. The patient will complete a PGI-I for symptom improvement, VSQ, I-QOL, QUID, OAB-q SF, FSFI, GAD-7 and PHQ-8. A vaginal exam, including a cough stress test and VHIS, will be performed. A vaginal swab will be collected for wet mount and examined microscopically for presence of lactobacillus. If the patient feels her symptoms have returned and she requests a repeat treatment this will be discussed with the investigator. If the investigator determines, in his/her clinical judgment, a treatment is appropriate the fCO₂ laser treatment will be performed. The patient will score discomfort using the VAS. The provider will score the difficulty of administering the treatment using the VAS.

VAS. If a treatment is given, the participant will be instructed to follow up with the practitioner per standard of care. Visit 10 will be the final visit.

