Laser treatment will be performed as per routine protocol. This includes intra-vaginal treatment based on atrophy level as based on VHIS score and treatment number.

Treatment	Atrophy	Treatment 1	Treatment 2	Treatment 3
Intravaginal	Severe (VHIS 6-15)	Energy: 7.5-10 mJ Density: 10%	Energy: 10 mJ Density: 10%	Energy: 10 mJ Density: 10%
	Moderate (VHIS 16-20)	Energy: 10 mJ Density: 10%	Energy: 10-12.5 mJ Density: 10-15%	Energy: 10-12.5 mJ Density: 10-15%
	Non-atrophic (VHIS >20)	Energy: 10 mJ Density: 10%	Energy: 12.5 mJ Density: 10-15%	Energy: 12.5 mJ Density: 15%

Laser is delivered at 6 points at each level of the vaginal wall: 12, 2, 4, 6, 8, and 10, o'clock of Hart's line. Delivery begins at the most proximal and the wand is retracted by 1 cm and another row of laser treatment is delivered. Number of levels is determined by patient vaginal length.

MEASURES

Cough Stress Test

During a vaginal exam, while the patient is in lithotomy or frog-legged position, the provider will ask the patient to cough and will look for visual signs of a urine leak. Any urine loss observed is indicative of a positive cough stress test.

Female Sexual Function Index (FSFI)

This validated questionnaire is a brief multidimensional scale for assessing sexual function in women. The scale has received initial psychometric evaluation, including studies of reliability, convergent validity, and discriminant validity²⁴.

Generalized Anxiety Disorder 7-item (GAD-7)

This validated questionnaire is used for screening for anxiety with good reliability with sensitivity of 89% and specificity of 82%, for use in clinical practice and in research²⁵.

Incontinence-Quality of Life (I-QOL)

This validated questionnaire is a commonly used self-report quality of life measure specific to urinary incontinence. This tool can be used to assess the impact of urinary problems and their treatment. The I-QOL has 22 questions with the following 3 subscales: avoid and limiting behaviors (items), psychosocial impacts (9 items), and social embarrassment (5 items). It is easily self-administered and takes about 5 minutes to complete.²³

Overactive Bladder Questionnaire-Short Form (OAB-q SF)

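### Does the laser settings table, which stops at Treatment 3, leave the repeat treatments at 1, 2 and 3 years so undefined that the plan must change?

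*Combined protocol and SAP*

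**What the plan says.** The Treatment section opens with "Laser treatment will be performed as per routine protocol" and continues: "This includes intra-vaginal treatment based on atrophy level as based on VHIS score and treatment number". The table below it has three rows by Vaginal Health Index Score (VHIS 6-15, 16-20 and above 20) and three columns, for Treatments 1, 2 and 3.

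Section II (Methodology) plans three treatments about six weeks apart and adds: "The patient will be offered a repeat treatment at 1, 2 and 3 years if initial treatment efficacy has decreased". The descriptions of Visits 6, 8 and 10 repeat one rule: "If the patient feels her symptoms have returned and she requests a repeat treatment this will be discussed with the investigator". The investigator's clinical judgment then decides whether the laser is used. At Visit 10, the last study visit, the text ends: "If a treatment is given, the participant will be instructed to follow up with the practitioner per standard of care".

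The Objectives and Outcomes table puts the primary endpoint at Week 16. It names Visit 4 (6 months) and Visit 10 (36 months) as secondary endpoints. Section V describes an observational study with no comparison group, descriptive statistics, subgroups by presenting complaint, and possible paired t tests from baseline to Visit 4.

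**The concern.** The settings need two keys: a VHIS row and a treatment number. VHIS is scored at Visits 6, 8 and 10, so the row is known at a repeat treatment. The column is not, because a fourth, fifth or sixth treatment has none. The text does not say whether the count restarts, stays at the last column or follows another rule.

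Two providers could therefore read the same protocol and deliver different settings at the same repeat. Repeats at Visits 6 and 8 come before the 36-month endpoint, and a repeat at Visit 6 also comes before Visits 7, 8 and 9. The long-term results could then describe a regimen whose later treatments a reader cannot reconstruct. The visit descriptions list the two visual analogue scores at each treatment but do not name delivered energy and density among the recorded items.

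Two smaller points concern the same table. The lowest possible VHIS total appears to have no row. The Measures section treats scores under 15 as atrophy, whereas the table's severe band runs to 15 and its moderate band from 16 to 20.

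**Working it through.** The plan states no figure to reproduce, so the check is a count followed by a comparison of table cells.

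**Treatments without a column**
- Initial treatments (Visits 1, 2, 3): 3. Possible repeats (Visits 6, 8, 10): up to 3. Maximum: 3 + 3 = 6.
- Table columns: 3. Without a column: 6 - 3 = 3, and 3/6 = 50%.
- By number of repeats (0, 1, 2, 3): 0/3 = 0%, 1/4 = 25%, 2/5 = 40%, 3/6 = 50%.

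**Repeats that can reach a study outcome**
- The Visit 10 repeat is described after that visit's questionnaires and examination, and no study visit follows. It can affect no outcome.
- Before the Visit 10 assessment a woman can have 3 + 2 = 5 treatments, of which 2 lack a column: 2/5 = 40%.
- The Visit 6 repeat also follows that visit's assessments. Of the seven follow-up visits (4 to 10), those after a possible repeat are Visits 7, 8, 9 and 10: 4 of 7.
- Week 16 and Visit 4 come before the first possible repeat, and so does every assessment in the paired t tests.

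**How far the column choice moves the setting**

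| VHIS row | Treatment 1 | Treatment 3 | Overlap |
|---|---|---|---|
| 6-15 | 7.5-10 mJ, 10% | 10 mJ, 10% | yes |
| 16-20 | 10 mJ, 10% | 10-12.5 mJ, 10-15% | yes |
| above 20 | 10 mJ, 10% | 12.5 mJ, 15% | no |

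Only the last row is disjoint: energy 12.5/10 - 1 = 25% higher, density 15/10 - 1 = 50% higher in relative terms.

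**Latitude already in the table**
- Cells with a range: VHIS 6-15 at Treatment 1; VHIS 16-20 at Treatments 2 and 3; VHIS above 20 at Treatment 2. That is 4 of 9.
- Within the VHIS 16-20 cells for Treatments 2 and 3, energy may run from 10 to 12.5 mJ (25%) and density from 10% to 15% (50% relative). One cell of the initial course therefore allows the same spread as the disjoint gap above.

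**Women involved**
- The documents give no repeat rate. If 10% to 50% of about 100 women repeat at Visit 6 (an assumption), 10 to 50 women reach later visits after a treatment with no stated column, before dropout.

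**The VHIS points**
- Five items scored 1 to 5 give a minimum of 5 x 1 = 5, assuming a simple sum. The table starts at 6, so one extreme total is uncovered.
- The atrophy cut-off in Measures is a label. No setting and no planned analysis uses it.

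**The case for a change.** The best case for acting is this. The protocol is prescriptive about Treatments 1 to 3, it offers the repeats itself, and Section III says investigators will follow the plan at all times. The monitoring plan checks protocol adherence, which cannot be judged for a setting that is not stated. Investigator judgment, as written, covers whether to treat and not at what setting. The routine protocol is neither cited nor reproduced. The row with disjoint settings is a realistic one, because women can enter with overactive bladder or recurrent urinary infection and need not have atrophy. Visit 10 is a named endpoint, and a clarifying sentence would cost almost nothing.

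Much of this stands. The omission is there, and the documents do not show that the routine protocol covers repeats. What does not follow is a change to the plan:

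- Differences between providers are not specific to repeats, since the table permits them in the initial course.
- For the 18- to 36-month descriptions, the fact that a woman was re-treated because her symptoms returned matters more than the setting used, and it would matter under any setting rule.
- Silence in the visit descriptions does not show that energy and density go unrecorded. The case report form is not among the documents, and the data-capture text in Section IV draws on the medical record and clinical assessments.
- Reporting how many women were re-treated, and at what settings if recorded, is ordinary description. It alters no analysis stated in Section V.

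**Conclusion.** The concern is right on the text but does not call for a change. The settings table has no column for repeat treatments, and the Treatment section and the repeat-visit text do not meet on this point. Reconciling them is an operational clarification for the sponsor's clinicians; I take no view on which setting applies.

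The statistical reach is small. At most 2 of 5 treatments before the 36-month assessment are affected, only in women re-treated at both Visit 6 and Visit 8, and the possible settings are disjoint in only one of three VHIS rows. The primary endpoint, the 6-month endpoint and the only named test are untouched. The long-term results are descriptive and have no comparison group, so no error rate, power figure or between-group contrast depends on the missing column. The uncovered VHIS total of 5 and the differing atrophy wording are clerical and change no result.

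This rests on reading the Visit 6, 8 and 10 descriptions in order, with assessments before any repeat laser treatment, and on providers applying their routine protocol consistently, which the documents do not let us verify. The number of women affected is unknown; 10 to 50 is an illustration under the assumed repeat rate.

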This validated measure evaluates overactive bladder symptom severity and health related quality of life (Coyne, 2015). Statistically significant correlations have been found between the OAB-q SF scales and other patient reported outcomes instruments. For example, higher levels of depressive symptoms as measured by the Center for Epidemiologic Studies Depression Scale (CES-D) were linearly related to higher levels of Symptom Bother (r 0.31, P<0.0001) and lower levels of health related quality of life (HRQL) on the OAB-q SF (r 0.35, P<0.0001). Both the Symptom Bother and HRQL scales easily differentiated between controls without overactive bladder (OAB), continent patients with OAB and incontinent OAB patients (P<0.0001).

Patient Global Impression of Improvement (PGI-I)

The Patient Global Impression of Improvement (PGI-I) will be used to evaluate the patients' perceptions of overall improvement after treatment. The questionnaire has been validated in several urogenital conditions²¹⁻²³.

Personal Health Questionnaire Depression score (PHQ-8)

This validated questionnaire is used for monitoring depression severity and response to treatment and can be used to screen for depression in at-risk populations.

Perception of Monetary Value

The laser treatments will be provided at no cost to the study participants. This questionnaire will be completed at the primary endpoint (16 weeks) and the 12 month visit.

Questionnaire for Urinary Incontinence Diagnosis (QUID)

This validated measure is used to evaluate improvement in stress-predominant urinary incontinence in women undergoing non-surgical treatment. It has been found to be valid and responsive with internal consistency and acceptable psychometrics characteristics for use in clinical trials²⁴.

Vaginal Health Index Score (VHIS)

The VHIS is a tool, used by providers, to determine if vaginal atrophy is present. Providers perform a vaginal exam and give a score of 1-5 (abnormal to normal, respectively) on each of the following vaginal parameters: elasticity, secretion/fluid volume, vaginal pH, integrity of the epithelium, and lubrication/moisture of the vaginal wall. A VHIS score less than 15 is indicative of vaginal atrophy.

Visual Analog Scale (VAS) for Pain/Discomfort

Patients will record their average pain score during treatment from 0 (no pain) to 10 (most severe pain imaginable) on a Visual Analog Scale for pelvic pain and discomfort.

Visual Analog Scale (VAS) for Procedure Difficulty

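### Do the different VHIS atrophy cut-offs in the Treatment table and the Measures section call for a change to the plan?

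*Combined protocol and SAP*

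**What the plan says.** The Treatment section bases the laser setting on the VHIS; it describes "intra-vaginal treatment based on atrophy level as based on VHIS score and treatment number". Its table has three rows: "Severe (VHIS 6-15", "Moderate (VHIS 16-20" and "Non-atrophic (VHIS >20" (each closing bracket is left off here). Each row lists an energy and a density for Treatments 1, 2 and 3.

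The Measures section describes the instrument. Providers "give a score of 1-5 (abnormal to normal, respectively) on each of the following vaginal parameters", and the parameters are "elasticity, secretion/fluid volume, vaginal pH, integrity of the epithelium, and lubrication/moisture of the vaginal wall". It then gives one threshold: "A VHIS score less than 15 is indicative of vaginal atrophy".

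In the Objectives and Outcomes table, the VHIS appears among the secondary outcomes as a change in vaginal health on examination. Section V plans descriptive statistics for all data, possible paired t tests on change in continuous measures from baseline to Visit 4, and subgroups by presenting complaint.

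**The concern.** The two sections put the boundary between atrophic and non-atrophic in different places: between 20 and 21 in the Treatment table, and between 14 and 15 in the Measures section. A score of 15 is the sharpest case. The table puts it in the severe row, yet it does not meet the Measures criterion for atrophy at all. The table also starts at 6, although five items with a minimum of 1 each can total 5, so the worst possible examination has no listed setting.

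Two things could be at stake. The first is treatment: the VHIS selects the energy and density, so an unclear category could mean an unclear setting. The second is reporting: anyone tabulating women as atrophic at baseline, or as no longer atrophic at follow-up, would get different counts depending on which section they used. A woman moving from 14 to 16 would lose her atrophy by the Measures cut-off but only move from severe to moderate by the table.

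**Working it through.** There is no stated sample size, power or test result to reproduce here. The check is to list the possible scores and then see where the plan uses each cut-off.

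**Inputs**
- Items: five, each scored 1 to 5 (Measures, VHIS).
- Measures cut-off: atrophy below 15.
- Treatment table rows: 6 to 15, 16 to 20, above 20.

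**Range of the score**
- Minimum: 5 × 1 = 5. Maximum: 5 × 5 = 25.
- Possible totals: 25 − 5 + 1 = 21.

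**Classification of each total**

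| Total | Treatment table | Measures cut-off | Number of totals | Result |
|---|---|---|---|---|
| 5 | no row | atrophy | 1 | no listed setting |
| 6–14 | severe | atrophy | 9 | agree |
| 15 | severe | not below 15 | 1 | labels differ |
| 16–20 | moderate | not below 15 | 5 | labels differ |
| 21–25 | non-atrophic | not below 15 | 5 | agree |

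Check: 1 + 9 + 1 + 5 + 5 = 21. Labels differ for 1 + 5 = 6 totals, and 1 total has no row.

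**Where each cut-off is used**
1. *Laser setting.* Only the Treatment table gives energy and density. Its rows print their own score ranges, and these do not overlap or leave a gap between 6 and 25. Read by number, 20 of the 21 totals lead to exactly one row. The Measures section assigns no setting, so its cut-off moves no one between rows. Only a total of 5 is left open.
2. *Eligibility.* The inclusion and exclusion criteria rest on symptoms, diagnoses and history. None uses a VHIS value.
3. *Secondary outcome.* The outcome is change as measured by the VHIS. For the woman moving from 14 to 16, the change is 16 − 14 = +2 whichever labels are used.
4. *Section V.* The possible paired t tests are on continuous measures, and the subgroups are by presenting complaint. No analysis by atrophy category, and no endpoint of atrophy resolved, is planned.
5. *Primary outcome.* This is the PGI-I, which does not involve the VHIS.

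**The uncovered score**
A total of 5 arises in only one way, with the lowest rating on all five items. The number of possible rating combinations is 5^5 = 3,125, and this is one of them. That ratio is not a probability, because the five items are likely to move together and the documents give no VHIS distribution. It shows only that the gap is confined to a single extreme examination.

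**The case for a change.** The strongest case for requiring a change rests on treatment, not on statistics. The Treatment section ties the setting to the atrophy level, so a provider could go by the label rather than the printed range. A provider who took the Measures cut-off at its word might regard a woman scoring 15 as not atrophic and look in the wrong row. The rows do differ: at Treatment 3 the severe row lists 10 mJ at 10% density and the non-atrophic row 12.5 mJ at 15%. The VHIS is recorded at all three treatment visits, so the lookup recurs. For a score of 5, adherence to the protocol cannot be monitored against a row that does not exist. Section V also promises frequencies and percentages for categorical characteristics, which leaves room for someone to tabulate atrophy status.

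Part of this stands. The labels do conflict, no text says that they serve different purposes, and a total of 5 has no setting. These are faults in the document, and the two sections must be reconciled.

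The rest does not carry far. The mislookup requires a provider to ignore the score range printed in the row and import a threshold from a section that assigns no settings. The Measures sentence is also weaker than the objection needs: it says that a low score points to atrophy, not that 15 or more rules it out. Reading it as a strict definition is reasonable, but it is an inference. The reporting problem would arise only if an analyst added a categorical VHIS summary that the plan does not name. Such a summary would have to state its cut-off in any case.

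**Conclusion.** The inconsistency is confirmed, but it does not call for a change to the design or the analysis. Six of 21 possible totals (15 to 20) have different atrophy labels in the two sections, and one total (5) has no row in the table. Neither fact alters a planned result: settings for totals 6 to 25 are unambiguous, eligibility does not use the VHIS, and change in the score does not depend on a cut-off.

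The fraction 7 of 21 should not be read as the share of women affected. It counts possible scores and combines two different matters. The share of women scoring 15 to 20, or exactly 5, cannot be worked out from the documents.

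What remains is a clerical correction: reconcile the wording of the two sections and account for the lowest score. The missing score lies immediately below the lowest band and is easily settled by a clarification from the clinical team, who must also decide which cut-offs and settings apply. Nothing here judges that question. Advice to analyse the VHIS as a continuous total would add nothing, since the plan already points that way.

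This conclusion rests on two assumptions: providers use the score ranges printed in the Treatment table, and no VHIS category is later made an endpoint. If one were, its cut-off would need to be fixed before the data are examined.
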